### **6.4.4.3 Group Therapy Sessions #5-10 (Weeks 6-8)**

Patients will undergo six group therapy sessions each 90-minutes long. Video footage of a random sampling of sessions will be analyzed with the HIM, SEGT-TG, IGMIPS and the GPIRS. Prior to each session, patients will be screened for adverse events and evaluated with the CSSR-S. Prior to sessions 5, 7 and 9, participants will fill out the CTC. After sessions 6, 8 and 10, participants will fill out the GQ. At the end of session 5, participants will fill out these questionnaires: CESD-R, DS-II, ICG, PCL-5, HARSI. After sessions 7 and 10, participants will fill out the DS-II and ICG.

## **6.4.5 Endpoint Assessments**

### **6.4.5.1 Endpoint (Week 8) Study Measures for Subjects**

Immediately after the last group therapy session (Week 8), patients will complete the AMAS, CESD-R, DS-II, DUFSS-5, ECR-M16, ICG, IOS, MQoL-RS, NR-6, PCL-5 SAHD, SCS-R, STAI, PTGI-SF, IPIP-OE-20, MAIA-R, HARSI, CTC, and CSS. A clinical rater will perform a MoCA and CGI for each subject.

### **6.4.5.2 Endpoint (Week 8) Study Measures for Caregivers/Important Others**

Patients' primary caregivers/important others will complete the CORF and CSS.

## **6.4.6 Post-treatment/Follow Up Assessments**

### **6.4.6.1 Focus Group (Week 10)**

Two weeks after the last group therapy session, subjects and their caregivers/important others will be invited to participate in a focus group wherein they will be asked to give feedback regarding their experiences in the study. Effort will be made to get both responders and non-responders to attend the focus groups. A clinical rater will administer the C-SSRS(Interval) to each subject. Prior to the focus group each participant will fill out the DS-II and ICG. This will be video-recorded for subsequent qualitative analysis. See Appendix C for focus group guide.

### **6.4.6.2 3-Month Follow-up for Subjects**

At 3 Months, patients will be mailed a packet with the following measures to be completed: AMAS, AUDIT, CESD-R, DS-II, DUDIT, DUFSS-5, ECR-M16, HARSI, ICG, MQoL-RS, NR-6, PCL-5, SAHD, SCS-R, STAI, PTGI-SF, IPIP-OE-20, MAIA-R, CTC, and the CSS. They will be called and encouraged to complete the packet.

### 6.4.6.3 3-Month Patients for Caregivers/Important Others

At 3 Months, primary caregivers/important others will be mailed a packet with the following measures: CORF and CSS. They will be called and encouraged to complete the packet.

#### 6.4.6.4 3-Month Qualitative Interviews

Between the Focus Group and the 3-month follow-up, subjects and caregivers/important others will be invited to participate in a semi-structured interview of their experience in the study. These interviews will be analyzed to detect potential mechanisms of the intervention as well as outcomes not addressed by the study measures. See Appendix C for interview guide.

## 6.5 Discontinuation of Therapy

The Investigator will withdraw a patient whenever continued participation is no longer in the patient's best interest. Reasons for withdrawing a patient include, but are not limited to, disease progression, the occurrence of an adverse event or a concurrent illness, a patient's request to end participation, a patient's non-compliance or simply significant uncertainty on the part of the Investigator that continued participation is prudent. There may also be administrative reasons to terminate participation, such as concern about a patient's compliance with the prescribed treatment regimen.

## 6.6 Dietary Restrictions

No dietary restrictions are included in the protocol.

## 6.7 Prohibited Medications

Patients are prohibited from using medications from the following classes while enrolled in the study:

- Serotonin Reuptake Inhibitors (SSRIs and SNRIs)
- Tricyclic Antidepressants (TCAs)
- Monoamine Oxidase Inhibitors (MAOIs)
- Atypical antidepressants (e.g., mirtazapine, nefazodone)
- Antipsychotics/Neuroleptics (typical and atypical)
- Anti-epileptics or mood stabilizers (e.g., lithium, valproate)
- Stimulants (e.g., methylphenidate, modafinil)
- Efavirenz (Sustiva, in Atripla)
- Insulin
- Non-topical corticosteroids
- Herbal supplements intended to affect mood or anxiety.

Conditional medication restrictions

- Trazodone
  - Trazodone  $\leq 50\text{mg}/24\text{hr}$  for insomnia is allowed, but not within 48hr of psilocybin session
- Benzodiazepines
  - PRNs are allowed, but not within 48hr of psilocybin session
  - "z-drugs" (e.g., zolpidem) are not allowed within 48hr of psilocybin session
- Non-benzodiazepine anxiolytics (e.g. gabapentin, buspar)
  - Gabapentin for neuropathic pain is allowed, but not within 48hr of psilocybin session

Individuals who at screening are excluded for taking contraindicated antidepressants, anxiolytics,

stimulants or herbal supplements can be re-screened for the study if—under the guidance of their usual physician—they successfully taper off these medications and demonstrate a period of psychiatric stability lasting at least 2 weeks. One exception to the required 2 week period is for individuals taking low dose TCAs ( $\leq 50$ mg imipramine equivalent) for reasons other than depression or anxiety (e.g., peripheral neuropathy or insomnia). These individuals may, under the guidance of their usual physician, taper off these medications and then be enrolled in the study once they are no longer taking the TCA.

## 6.8 Study Clinicians

Study clinicians (group therapists and treatment session guides) will be approved by a panel consisting of: [name] (PI), [name] (UCLA psilocybin team, and lead clinical supervisor for UCSF the team), [name] (UCSF psilocybin team), and [name] (Johns Hopkins psilocybin team). Group therapists and treatment session guides will all be licensed clinicians (MD, RN, NP, MFT, LCSW, PhD, PsyD, Chaplain, etc) in the state of California; an exception will be made if the person is unlicensed but currently enrolled in a clinical training program and has had sufficient clinical exposure, according to the judgment of the above-mentioned panel. The selection of therapists/guides will give preference to those who have: 1) prior clinical experience working with the study population; 2) have demographic similarities to the study population (age, gender, sexual orientation); 3) prior experience conducting group therapy; 4) prior experience working with individuals under the influence of psychedelics either in research settings or harm-reduction settings (such as the Zendo Project); 5) have completed the CIIS certificate program in Psychedelic-assisted Psychotherapy and research; 6) must have completed CITI training and have been added to the study IRB.

Group therapist pairs will consist of one lead and one secondary therapist. The lead must have had significant experience as a group therapy leader; the secondary must have some experience as a group therapy leader. Group therapists will undergo at least 16 hours of training in Supportive-Expressive Group Therapy (SEGT) by studying SEGT training videos, the SEGT adherence rating scales that will be used in the study, and the 3 following SEGT manuals: the original manual for metastatic breast cancer patients [75], the manual for brief SEGT in newly diagnosed breast cancer patients [76], and the adaptation by Maldonado et al for patients with AIDS [78]. All group therapists will undergo at least one 'dry run' session of the SEGT method prior to starting a group.

Each subject will have 2 guides working with them in their drug treatment day (not necessarily one male and one female). At least one of the treatment session guides will be one of the subject's group therapy co-therapists. Treatment session guides will undergo instruction by [name] and/or [name]. Overall clinical supervision will be a responsibility shared by [name] (PI), [name] (lead medical supervisor) and [name] (lead psychotherapy supervisor). Clinical consultation will be available from others involved in the study, such as [name], Co-Investigator of this study and founder and of the UCSF Alliance Health Project, as well as [name], a study clinician who is a staff psychiatrist at the SFVA with many years experiencing running psychotherapy groups for gay men in San Francisco.

Clinical supervision specifically related to psilocybin, and SEGT, will happen in the form of debriefing sessions after every study visit. [name] will be an in-the-room observer of the group therapy sessions to take notes and later discuss with the group therapists their adherence to the SEGT method and its current adaptation to the psilocybin trial. [name] and [name] will review video of treatment sessions and discuss the technique observed with the

individual session guides on an as needed basis. Video segments of group therapy sessions and psilocybin treatment sessions will be used for discussion in a periodic supervision workshop to be held after the completion of each group therapy cohort and which all study clinicians will be highly encouraged to attend. The number of supervision sessions a study clinician is required to attend to maintain eligibility to work on the study will be up to the discretion of the clinical supervisors.

## 7 Reporting and Documentation of Results

### 7.1 Evaluation of Safety and Feasibility

The assessment of safety and feasibility will be informed by surveillance of adverse events in all patients who enroll in the study. The study will use the NIH Division of AIDS Table of Grading of Severity of Adult and Pediatric Adverse Events V2.0 for reporting of adverse events. Analyses of feasibility and acceptability will also be informed by rates of patient recruitment and retention, therapist protocol adherence, self-report measures (CrEQ and CSS), and spontaneous feedback from subjects, caregivers/important others, and study therapists.

### 7.2 Evaluation of Efficacy

We will evaluate for trends in changes of group mean measures of demoralization, complicated grief, depression, anxiety, and other constructs mentioned above. These evaluations will consist of self-report measures (e.g., DS-II) and observations from caregivers/important others and clinical raters (e.g., CORF and CGI).

### 7.3 Definitions of Adverse Events

#### 7.3.1 Adverse Event

An adverse event (also known as an adverse experience) is defined as any untoward medical occurrence associated with the use of a drug in humans, whether or not considered drug related. More specifically, an adverse event (can be any unfavorable and unintended sign (e.g., an abnormal laboratory finding), symptom, or disease temporally associated with the use of a drug, without any judgment about causality. An adverse event can arise from any use of the drug (e.g., off-label use, use in combination with another drug) and from any route of administration, formulation, or dose, including an overdose.

#### 7.3.2 Adverse reaction

An adverse reaction is defined as any adverse event caused by the use of a drug. Adverse reactions are a subset of all suspected adverse reactions for which there is reason to conclude that the drug caused the event.

##### 7.3.2.1 Suspected

A suspected adverse reaction is defined as any adverse event for which there is a reasonable possibility that the drug caused the adverse event. For the purposes of IND safety reporting, “reasonable possibility” indicates that there is evidence to suggest a causal relationship between the drug and the adverse event. A suspected adverse reaction implies a lesser degree of certainty about causality than an adverse reaction.

##### 7.3.2.2 Unexpected

An adverse event or suspected adverse reaction is considered *unexpected* if it is not listed in the investigator brochure or package insert(s), or is not listed at the specificity or severity that has been observed, or, if an investigator brochure is not required or available, is not consistent with the risk information described in the general investigational plan or elsewhere in the current application.

“Unexpected,” as used in this definition, also refers to adverse events or suspected adverse reactions that are mentioned in the investigator brochure as occurring with a class of drugs or

as anticipated from the pharmacological properties of the drug, but are not specifically mentioned as occurring with the particular drug under investigation.

Adverse events that would be anticipated to occur as part of the disease process are considered *unexpected* for the purposes of reporting because they would not be listed in the investigator brochure.

### 7.3.2.3 Serious

An adverse event or suspected adverse reaction is considered *serious* if, in the view of either the investigator or sponsor, it results in any of the following outcomes:

- Death
- Life-threatening adverse event
- Inpatient hospitalization or prolongation of existing hospitalization
- A persistent or significant incapacity or substantial disruption of the ability to conduct normal life function
- Congenital anomaly/birth defect

Important medical events that may not result in death, are life-threatening, or require hospitalization may be considered serious when, based upon appropriate medical judgment, they may jeopardize the patient or subject and may require medical or surgical intervention to prevent one of the outcomes listed in this definition. Examples of such medical events include allergic bronchospasm requiring intensive treatment in an emergency room or at home, blood dyscrasias or convulsions that do not result in inpatient hospitalization, or the development of drug dependency or drug abuse.

### 7.3.2.4 Life-threatening

An adverse event or suspected adverse reaction is considered *life-threatening* if, in the view of either the investigator or sponsor, its occurrence places the patient or subject at immediate risk of death. It does not include an adverse event or suspected adverse reaction that, had it occurred in a more severe form, might have caused death.

## 7.4 Recording of an Adverse Event

All adverse events will be entered into UCSF REDCap, whether or not the event is believed to be associated with use of the study drug. Data about these events and their severity will be recorded using the NIH Division of AIDS Table of Grading of Severity of Adult and Pediatric Adverse Events V2.0.

The Investigator will assign attribution of the possible association of the event with use of the investigational drug, and this information will be entered into UCSF REDCap using the classification system listed below:

Relationship	Attribution	Description
Unrelated to investigational drug/intervention	Unrelated	The AE is clearly NOT related to the intervention
	Unlikely	The AE is doubtfully related to the intervention
Related to investigational drug/intervention	Possible	The AE may be related to the intervention
	Probable	The AE is likely related to the intervention
	Definite	The AE is clearly related to the intervention

Signs or symptoms reported as adverse events will be graded and recorded by the Investigator. When specific adverse events are not listed in the above NIH DAIDS Table of Grading of Severity, they will be graded by the Investigator as *none*, *mild*, *moderate* or *severe* according to the following grades and definitions:

- Grade 0 No AE (or within normal limits)
- Grade 1 Mild: Mild symptoms causing no or minimal interference with usual social & functional activities with intervention not indicated
- Grade 2 Moderate: Moderate symptoms causing greater than minimal interference with usual social & functional activities with intervention indicated
- Grade 3 Severe: Severe symptoms causing inability to perform usual social & functional activities with intervention or hospitalization indicated
- Grade 4 Potentially life-threatening: Potentially life-threatening symptoms causing inability to perform basic self-care functions with intervention indicated to prevent permanent impairment, persistent disability, or death
- Grade 5 Death related to AE

## 7.5 Follow-up of Adverse Events

All adverse events will be followed with appropriate medical management until resolved. Patients removed from study for unacceptable adverse events will be followed until resolution or stabilization of the adverse event.

## 7.6 Adverse Events Monitoring

All adverse events, whether or not unexpected, and whether or not considered to be associated with the use of the study drug, will be entered into UCSF REDCap, as noted above.

The Investigator will assess all adverse events and determine reportability requirements to the Data and Safety Monitor (DSM) and UCSF's Institutional Review Board, the Committee on Human Research (CHR); and, when the study is conducted under an Investigational New Drug Application (IND), to the Food and Drug Administration (FDA) if it meets the FDA reporting criteria.

In addition, all adverse events and suspected adverse reactions considered "serious," entered into UCSF REDCap will be reviewed and monitored by the Data and Safety Monitor on an

ongoing basis, discussed at DSM meetings which take place after each therapy group completes the 8-week intervention.

## **7.7 Expedited Reporting**

### **Reporting to the Data and Safety Monitor**

If a death occurs during the treatment phase of the study or within 30 days after the last administration of the study drug(s) and it is determined to be related either to the study drug(s) or to a study procedure, the Investigator or his/her designee must notify the DSM within 1 business day of knowledge of the event. The contact may be by phone or e-mail.

### **Reporting to UCSF Committee on Human Research (Institutional Review Board)**

The Principal Investigator must report events meeting the UCSF CHR definition of “Unanticipated Problem” (UP) within 10 business days of his/her awareness of the event.

### **Expedited Reporting to the Food and Drug Administration**

If the study is being conducted under an IND, the Sponsor-Investigator is responsible for determining whether or not the suspected adverse reaction meets the criteria for expedited reporting in accordance with Federal Regulations (21 CFR §312.32).

The Investigator must report in an IND safety report any suspected adverse reaction that is both serious and unexpected. The Sponsor-Investigator needs to ensure that the event meets all three definitions:

- Suspected adverse reaction (as defined in 7.3.2.1)
- Unexpected (as defined in 7.3.2.2)
- Serious (as defined in 7.2.3.3)

If the adverse event does not meet all three of the definitions, it should not be submitted as an expedited IND safety report.

The timeline for submitting an IND safety report to FDA is no later than **15 calendar days** after the Investigator determines that the suspected adverse reaction qualifies for reporting (21 CFR 312.32(c)(1)).

Any unexpected fatal or life-threatening suspected adverse reaction will be reported to FDA no later than **7 calendar days** after the Investigator’s initial receipt of the information (21 CFR 312.32(c)(2)).

Any relevant additional information that pertains to a previously submitted IND safety report will be submitted to FDA as a Follow-up IND Safety Report without delay, as soon as the information is available (21 CFR 312.32(d)(2)).

### **Reporting to Pharmaceutical Companies providing Study Drug**

Serious adverse reactions will be reported to the Heffter Research Institute and the Usona Institute, which are consultants for this study.

## **8 Statistical Considerations and Evaluation of Results**

### **8.1 Study Design**

This open-label single-arm mixed-methods pilot study will use descriptive statistics and qualitative methods to evaluate safety and feasibility in terms of rates of adverse events, patient recruitment and retention, and feedback on the intervention's utility, content and duration. Given the small sample size of this study, small-to-medium effect sizes will likely be undetectable; and so descriptive statistics will be used to report changes in mean measures at baseline compared to the endpoint, and again at the 3-month follow-up. Exploratory ANOVAs will also be done to model changes in therapeutic process values (e.g., group cohesion) over time. Qualitative thematic analysis will also be used to evaluate verbal and written reports of patient and caregiver/important other experiences with the study in order to optimize implementation of the intervention in larger, future trials.

#### **8.1.1 Randomization**

No randomization procedures will be used.

#### **8.1.2 Stratification Factors**

No stratification procedures will be used.

### **8.2 Determination of Sample Size and Accrual Rate**

#### **8.2.1 Sample Size and Power Estimate**

This pilot study of the safety and feasibility of psilocybin-assisted group therapy aims to enroll at least 18 subjects, and will have a maximum total sample size of 36. We estimate needing to enroll 18 subjects given attrition rates of up to 45% reported in trials of other group therapies for existential distress in palliative care patients [114]. For comparison, four different safety and feasibility pilot studies of psilocybin-assisted psychotherapy have been conducted over the last two decades, and have included 9, 10, 12 and 15 patients each [18, 107, 108, 110]. Four recently published feasibility pilot studies of meaning-focused group psychotherapies for palliative care patients have included 5, 11, 11, and 16 patients each [40, 178-180].

Group therapy studies should include at least 2 groups of at least 4-6 members [135], so we plan to have at least 8 subjects complete the intervention. We expect to be able to enroll at least 6 subjects every 6 months.

Because the proposed study is a pilot focused on investigating safety and feasibility, power calculations for efficacy measures are not indicated. Pilot studies are often used to estimate values that are then utilized in power calculations for full-scale trials. Indeed, we will estimate effect size (ES) and the intraclass correlation coefficient (ICC) [132] for the intervention based on our preliminary efficacy results. Group psychotherapy trials generally require large sample sizes to demonstrate statistical significance in change in efficacy measures given the likely interdependence of clinical outcomes when interventions are delivered in groups [132, 133]. Thus, future full-scale trials can utilize our estimates to derive adequate, and likely large, sample sizes.

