Unique Aspects of this Study	
This trial will be the first clinical trial of psilocybin-assisted psychotherapy for LTAS. It will also be the first modern trial of psilocybin-assisted group psychotherapy. It will be the first study of psilocybin-assisted psychotherapy for existential distress that will employ an evidence-based psychotherapy in the non-drug therapy sessions. The study will provide the first safety data for the use of this intervention in LTAS. It will not only yield preliminary data on the potential efficacy of this novel intervention, but it will also be the first study to employ both validated quantitative measures and qualitative methods in the analysis of the psychotherapeutic processes germane to psilocybin-assisted psychotherapy. It will also be the first clinical trial of psilocybin-assisted psychotherapy to assess the impact of the intervention on quality of life in partners/caregivers of LTAS. In anticipation of larger, better powered trials, clinical outcomes from this Phase I study will be used to produce the first estimates of effect size of this novel treatment for demoralization in palliative care patients.

------------------------------	--

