## 1 Introduction

We propose to conduct a clinical trial of psilocybin-assisted psychotherapy for demoralization in Long-term AIDS Survivors (LTAS). This will be the first trial of psilocybin-assisted psychotherapy specifically for people living with HIV (PLH) and it will be the first modern trial of psilocybin-assisted *group* psychotherapy for any indication. The study will consist of three groups of six gay-identified HIV-seropositive men  $\geq 50$  years of age who were diagnosed with HIV prior to 1996 and who have moderate-to-severe demoralization [27] [13]. Each subject will undergo 8 weeks of a modified form of Supportive-Expressive Group Therapy [25] and one individual psilocybin treatment session [24] half-way through the intervention. Quantitative and qualitative measures of psychotherapeutic process will be used to explore the mechanisms by which this novel therapy seems to work, particularly on the interpersonal level. Quantitative and qualitative measures will assess changes in quality of life of the partners/caregivers of subjects undergoing the intervention. This study will contribute to the available data on the safety, feasibility and efficacy of psilocybin-assisted psychotherapy for existential distress in palliative care patients, and importantly will provide the first of such data on a palliative care population other than cancer patients [28].

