#### *Rationale for Supportive-Expressive Group Therapy*

While prior trials of psilocybin-assisted psychotherapy for existential distress in palliative care patients have followed a standard drug administration safety protocol, they have not used manualized psychotherapies in the non-drug therapy sessions; our study will be the first to do this, which should enhance generalizability of the results. The format and content of SEGT are appropriately flexible for incorporating individual psilocybin sessions during the course of therapy, and including psychoeducation on psilocybin in the preparatory sessions. The focus of SEGT on expressing emotions and enhancing communication with caregivers is expected to be helpful in integrating psilocybin experiences [118]. Psilocybin has been shown to enhance access to positive emotional memories [141] and to increase the personality trait of openness [106], and this should support SEGT's aim of increasing awareness of one's emotions and openness to new experiences. Because the primary aim of this pilot trial is to assess safety and feasibility of this modality—and assessing efficacy is a secondary aim—no control group of traditional SEGT will be included in the study. For the rationale on why psilocybin monotherapy (without an adjunctive psychotherapy) will not be offered as control condition, see above.

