#### 2.2.2 Exploratory Endpoints

Preliminary efficacy will be assessed with the primary clinical outcome measures:

- Change in demoralization will be defined as the difference in pre-treatment, post-treatment, and 3-month follow-up scores of the Demoralization Scale-II.
- Change in complicated grief will be defined by the difference in pre-treatment, post-treatment, and 3-month follow-up mean scores of the Inventory of Complicated Grief.

Preliminary efficacy will also be explored with the following secondary endpoints (See Section 5 for details on individual measures):

- Change in ART medication adherence will be defined as the difference in pre-treatment, post-treatment, and 3-month follow-up mean scores of the ART Medication Adherence Scale.
- Change in depression will be defined by the difference in pre-treatment, post-treatment, and 3-month follow-up mean scores of the Center for Epidemiologic Studies Depression Scale—Revised. Change in subject quality of life will be defined by the difference in pre-treatment, post-treatment, and 3-month follow-up mean scores of the McGill Quality of Life Questionnaire—Revised.
- Change in desire for hastened death will be defined as the difference in pre-treatment, post-treatment, and 3-month follow-up mean scores of Schedule of Attitudes towards Hastened Death.
- Change in anxiety will be defined as the difference in pre-treatment, post-treatment, and 3-month follow-up mean scores of the State-Trait Anxiety Inventory.
- Change in social support will be defined as the difference in pre-treatment, post-treatment, and 3-month follow-up mean scores of the Duke/UNC Functional Social Support Questionnaire-5.
- Post-traumatic growth due to the intervention will be defined by post-treatment and 3-month follow-up mean scores of Post-Traumatic Growth Inventory—Short Form.
- Change in PTSD symptoms will be defined as the difference in pre-treatment, post-treatment, and 3-month follow-up mean scores of the PTSD Checklist-5.
- Change in global clinical status will be defined as the difference in pre-treatment and post-treatment mean scores of the Clinical Global Impressions Scale completed by an clinical rater.
- Change in openness to experience will be defined as the difference in pre-treatment, post-treatment, and 3-month follow-up mean scores of the International Personality Item Pool—Openness to Experience-20 scale.

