### **3.6 Randomization Procedures**

Patients will not be randomized; this is an open-label pilot trial with one treatment arm.

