### **8.5.1 Exploratory Analyses**

Change in efficacy measures from pre-treatment to post-treatment to 3-month follow-up will be analyzed with descriptive statistics to represent trends in mean levels. Recognizing that the calculations will likely be underpowered, we will also perform ANOVAs of the secondary outcome measures. To assist in gauging the clinical relevance of these data relative to measurement error, and to overcome some of the limitations of the study's small sample size, Reliable Change Indices (RCI) will be calculated [181]. Data from efficacy measures will also be used to estimate effect sizes and intraclass correlation coefficients for use in larger, future studies.

Change in process measures (e.g., the HIM, QPIRS and GQ) over time will be analyzed with ANOVAs to assess the slopes of individual participants and of the whole sample.

Qualitative thematic analyses will be conducted according to the methods outlined in Section 6.3. Iterative inductive analyses will be performed with the aid of NVivo analytical software.

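### Section 8.2.1 says future trials can derive adequate sample sizes from this pilot's effect size and ICC; one uncontrolled arm and two to six therapy groups cannot support that

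*Combined protocol and SAP*

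**What the plan says.** Section 8.2.1 states that no efficacy power calculation is needed for a safety and feasibility pilot. It then says the preliminary efficacy results will supply an effect size and an ICC, and ends: "Thus, future full-scale trials can utilize our estimates to derive adequate, and likely large, sample sizes".

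Two other places point the same way but promise less. The abstract (Unique Aspects of this Study) says "clinical outcomes from this Phase I study will be used to produce the first estimates of effect size of this novel treatment". Section 8.5.1 says "Data from efficacy measures will also be used to estimate effect sizes and intraclass correlation coefficients for use in larger, future studies". Neither claims that the resulting sample sizes would be adequate.

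On the design, section 3.6 says "this is an open-label pilot trial with one treatment arm", and section 1.3 (Rationale for Supportive-Expressive Group Therapy) says "no control group of traditional SEGT will be included in the study". Section 2.2.2 sets the effect as change over time: "Change in demoralization will be defined as the difference in pre-treatment, post-treatment, and 3-month follow-up scores of the Demoralization Scale-II". On the number of groups, the Introduction says "The study will consist of three groups of six gay-identified HIV-seropositive men". Section 3.2 permits from two groups of at least four completers to six groups of six.

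No section plans an interval for the effect size or the ICC, names the ICC model or the standardiser of the effect size, or labels the effect size as uncontrolled.

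**The concern.** A controlled full-scale trial of a group-delivered treatment is sized on two inputs: the difference expected between arms, and the ICC that sets the inflation for clustering. The pilot observes no between-arm difference. Its pre-post change combines any drug effect with ten group therapy sessions, expectancy and natural course. It may also include regression to the mean, since entry requires a Demoralization Scale-II score of 8 or higher and section 6.4.3.1 lets a screening score taken within a week stand as baseline.

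The ICC is estimated from between-group variance, which has 2 degrees of freedom with three groups, 1 with two and 5 with six.

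A later team that took the sentence in 8.2.1 at its word could size its trial on an effect that is too large and an ICC that is little more than noise, with nothing in the pilot's planned reporting to warn it.

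**Working it through.** **The plan's own figure.** The only sample-size figure is the target of 18. Section 8.2.1 gives at least 8 completers and attrition of up to 45%: 8 / (1 - 0.45) = 14.5, so 15, or 18 in whole groups of six (the rounding to whole groups is my reading). The target is a feasibility figure and uses neither an effect size nor an ICC, so nothing below changes it.

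**Assumed inputs.** The documents give no alpha, power, effect size, SD or ICC. I assume two-sided alpha 0.05, 80% power, outcome SD 1, a within-group d of 1.0 and an ICC of 0.10. The numbers of groups come from the Introduction and section 3.2.

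**Effect size.** If a control arm would show a fraction f of the within-group change, the between-arm effect is d(1 - f). For a two-sample t-test, ignoring clustering, d = 1.0 needs 17 per arm. The power of that trial at the effect actually present is:

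| Share f also seen in controls | Between-arm d | Power with 17 per arm | Needed per arm for 80% |
|---|---|---|---|
| 0 | 1.00 | 81% | 17 |
| 1/4 | 0.75 | 56% | 29 |
| 1/2 | 0.50 | 29% | 64 |
| 3/4 | 0.25 | 11% | 253 |

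The pilot has no control arm, so it cannot say which row applies.

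**ICC.** For k groups of m, the one-way ANOVA estimate is (F - 1) / (F + m - 1), with k - 1 and k(m - 1) degrees of freedom.

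- *Chance of an estimate at or below zero.* This is P(F < 1/θ), with θ = (1 + (m - 1)ρ) / (1 - ρ). At ρ = 0.10 and m = 6, θ = 1.5 / 0.9 = 1.667. For three groups, P(F(2,15) < 0.6) = 0.44. For six groups, P(F(5,30) < 0.6) = 0.30.
- *Exact 95% interval around an observed 0.10.* Divide the observed F by the upper and lower 2.5% points of the F distribution and convert back to an ICC. For three groups of six, the observed F is 1.667 and the 2.5% points are 4.765 and 0.02536. The limits for F are 0.350 and 65.7, so the ICC limits are (0.350 - 1) / (0.350 + 5) = -0.12 and (65.7 - 1) / (65.7 + 5) = 0.92.

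| Groups | 95% interval for an observed ICC of 0.10 | Design effect for groups of six, negative ICC set to 0 |
|---|---|---|
| two of four | -0.26 to 0.997 | 1 to 6.0 |
| three of six | -0.12 to 0.92 | 1 to 5.6 |
| six of six | -0.08 to 0.61 | 1 to 4.0 |

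The design effect is 1 + 5 × ICC; for three groups of six, the unrounded upper limit of 0.915 gives 1 + 5 × 0.915 = 5.6. Even at the permitted maximum, the interval runs from no inflation to a fourfold one.

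**The case against.** The strongest reply is that nothing in this trial depends on either estimate. The primary aims are safety and feasibility, efficacy is exploratory, and the planning values are not among the stated objectives. Section 8.1 admits that small-to-medium effects will probably go undetected. Section 8.2.1 itself stresses interdependence within groups and expects large samples, so a careful reader would be unlikely to take an ICC of zero at face value. The text says only that future trials can use the estimates; it does not say that they should use bare point estimates or treat pre-post change as a between-arm contrast. All of this stands, and it limits the weight of the point. It does not remove it: the admission in 8.1 concerns detection in this trial, and no passage qualifies later use of the estimates.

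The future design is not stated. For a single-arm successor, pre-post change would be the right quantity, though imprecise: at n = 18 an observed standardised change of 0.8 has a 95% interval of 0.26 to 1.32, ignoring clustering. The ICC half stands for either design.

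A reader might infer that the successor trial will probably be underpowered, or that the ICC will come out at zero nearly half the time. The documents support neither. Power depends on a control response that they do not give, and the share of estimates at or below zero falls to 30% with the six groups that the plan permits. Nor do the abstract and 8.5.1 repeat the claim of adequacy; only the last sentence of 8.2.1 makes it.

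**Conclusion.** The concern holds for one sentence and for the reporting that should go with it. Section 8.2.1 credits the pilot's effect size and ICC with a property that one arm and two to six groups cannot give them.

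The effect-size half assumes a controlled successor. Its size is a range: 56% to 11% power for a trial of 17 per arm, depending on whether controls would show a quarter or three quarters of an assumed change of 1.0 SD. The ICC half needs no assumption about a control arm, and it survives at every permitted number of groups.

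The point should be corrected because planning values are something the pilot says it will hand on. It does not touch the safety and feasibility conclusions or the enrolment target, and it is not a reason to enlarge the pilot.

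**What to change.** - **Section 8.2.1:** replace the last sentence. Say that the effect size is uncontrolled within-person change and should not be used as a between-arm effect, and that future sizing should use a justified target difference and a range of ICC values rather than this pilot's point estimate.
- **Section 8.5.1:** report the effect size and the ICC with 95% intervals, as descriptive. Baseline SD, pre-post correlation, retention and accrual may be carried forward as planning inputs. The correlation needs its own interval: at n = 18 an observed 0.5 has a 95% interval of about 0.04 to 0.78 (Fisher z).
- **Abstract:** add only the word uncontrolled to the effect-size statement.

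The cost is some wording and the intervals, and the pilot promises less. No visit, measure or participant is added.
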